5.1 Small Airways Dysfunction Tool (SADT) questionnaire

The SADT questionnaire was developed for patients with asthma and consist of 63 items. SADT items were scored on a 3-point scale (no, yes, unknown)¹⁰. The items reflect specific signs and symptoms which could be suggestive for Small Airways Dysfunction (SAD) or could reflect signs and symptoms that are suggestive for less SAD.

A shorter version of the SADT for asthma with items more tailored to COPD patients will be devised as a part of study. Input from the scientific advisory board (in part the steering committee of the ATLANTIS study¹⁸.) and patient interviews (described in chapter 5.4) will be used. The SADT for COPD (SADT-c) will contain approximately 15 questions.

5.2 Oscillometry

Oscillometry is a non-invasive technique for assessing lung function, as it requires only 45-60 seconds of tidal breathing to measure the mechanical properties of the respiratory system. This makes the measurement suitable for patients of all ages and with severe respiratory conditions. It also reduces the number of errors as compared to other methods (e.g., spirometry). Oscillometry can be used to evaluate airway resistance, reactance, and compliance, insights that are challenging to obtain with other methods. This quality makes oscillometry especially sensitive for obstructive diseases like asthma and COPD, and correlations with physiological small airways dysfunction have also been shown^{8,18,19}.

The Ambulatory Lung Diagnosis System (ALDS), manufactured by Lothar MedTec, can be used to perform oscillometry and spirometry (Figure 2). The ALDS follows the European Respiratory Society (ERS) technical standards for measurement and reporting of oscillometry.

SCOOP

[figure not shown]

Figure 2. Oscillometry and spirometry performed with the ALDS system. A) Schematic overview of oscillometry process and decision support by the ALDS. B) Example of a report generated by the ALDS.

The measurement is performed using approximately 45-60 seconds of tidal breathing. Three measurements of 15 seconds will be performed, during which the patient will calmly breathe in and out while wearing a nose clip. This requires no specific training or effort from patients. The healthcare professional (HCP) can be trained within 15 minutes on how to perform the measurement and the requirements for accurate measurement. The ALDS has built-in quality control measures and provides feedback if quality is not sufficient.

Reversibility testing can also be conducted using the ALDS device, in addition to standard oscillometry measurements.

5.3 Additional AC/DC questions

The Asthma/COPD Differentiation Classification (AC/DC) tool is a machine learning algorithm for the differential diagnosis of asthma or COPD based on 12 variables. Except for two of the twelve variables, all information is already available in the data standard collected by the study sites. Two additional questions will be collected to be able to run the AC/DC algorithm. Namely:

- 1. Diagnosis of allergic rhinitis
- 2. Diagnosis of chronic rhinitis

5.4 Cognitive interviewing

The aim of cognitive interviewing is to assess how participants process information to comprehend, respond to the questions and to determine whether new items are needed to complete the SADT-c.

A total of ten to fifteen patients with COPD and SAD who are native Dutch speakers will be invited to participate in cognitive interviews about the SADT-c with a clinician. Patients are to be representative of the real-world population of patients with COPD as much as possible. The interviewer will report the answers anonymously and will discuss the results of the interviews in a meeting with a member of the GPRI team.

The followings steps will be followed to conduct a cognitive interview:

- The clinician will present a form with the patient-reported version of the questions under study to the patient and will ask the patient to read it and answer the question. The clinician will record the answer.
- **2.** The clinician will ask the scripted questions.
- **3.** The clinician will investigate whether there are additional items that could describe SAD.
- **4.** The clinician will also report all other issues / comments that were raised during the interview.

The following scripted questions will be asked:

- In your own words, what do you think this question is asking?
- Was this question easy to understand? Are there any specific words that are difficult to understand?
- Was there anything else about the question that was unclear to you?
- Suppose you would be talking with others about /question/, which word or phrase would you use?
- Is there anything else you would like to share about this question?

6. METHODS

6.1 Study endpoints

6.1.1 Main study endpoint

The primary endpoint is the predictive value of SADT-c for detecting SAD in patients with COPD.

Required variables:

- Diagnosis of Asthma/COPD service
- SAD status defined as R5–R20 > upper limit of normal (ULN)¹
- SADT question results
- Patient characteristics
 - o Age
 - o Sex
 - o Height
 - Body Mass Index (BMI)
 - Age at diagnosis
- Oscillometry and spirometry results

6.1.2 Secondary study endpoints

The secondary endpoints are:

- 1. Predictive value of SADT-a bronze model for SAD in COPD.
- 2. Agreement between SADT-c results and disease parameters.
- 3. Content validity and reliability.
- 4. Relative predictive value of SADT-a versus SADT-c for SAD in COPD defined as R5– R20 > ULN¹
- 5. Agreement between triage diagnoses from oscillometry and spirometry.
- 6. Relative usability of spirometry and oscillometry.

Required variables:

- 1.
- Triage diagnosis of Asthma/COPD service
- SAD status based on oscillometry test (R5-R20)
- SADT question 8
- Patient characteristics (bronze model)
 - o Age
 - o Sex
 - o Height
 - o Body Mass Index (BMI)
 - Age at diagnosis
- 2.
- Triage diagnosis by Asthma/COPD service
- SAD status based on oscillometry test (R5-R20)
- Lung function results

- Asthma/COPD service collected questionnaires and patient characteristics (as described in chapter 5)
- SADT-c variables
- Patient characteristics bronze model
- 3.
- Cognitive interviews
- SADT-c results
- 4.
- Predictive value SADT-a different models
- Predictive value SADT-c different models
- 5.
- Panel expert diagnoses (spirometry)
- Panel expert diagnoses (oscillometry)
- Patient characteristics
- Difficulty to diagnose (scale)
- 6.
- Operator opinion
- Expert interpreter opinion
- Duration of measurement
- Patient burden

6.1.3 Exploratory study endpoints

Diagnostic performance of AC/DC tool compared to expert panel diagnosis.

Required variables:

- AC/DC tool
- FEV1
- FEV1/FVC
- Smoking pack-year
- Age at onset of respiratory disease
- Body mass index
- Dyspnea
- Wheeze
- Cough
- Diagnosis of allergic rhinitis
- Current smoker
- Never smoked
- Diagnosis of chronic rhinitis

6.2 Study procedures

Participants will be invited by the study site for a diagnostic or control visit to perform a lung function test. Together with the invitation for this visit, information about the SCOOP study is sent. The recipient will have the option to make their interest or disinterest in the study known before their visit (but this is not required). The study flow is presented in document E₃.

During the regular diagnostic or control visit participants that did not reply to the initial information and participants that have shared their interest will be further informed about the SCOOP study and asked whether they would like to participate. In case a person does not want to participate in the study, the Asthma/COPD visit will continue as usual. In case a person does want to participate in the study, the study activities will be added to the regular visit.

After signing informed consent, the visit will include a (pre-)oscillometry measurement followed by a (pre-)spirometry measurement. In case of a diagnostic visit the participant will use Salbutamol followed by a post-oscillometry and post-spirometry measurement after a 15-minute wait time. During the wait time, or after the measurements in case of a control visit, the participant is asked to fill in the SADT-c questionnaire and two additional study questions.

10-15 participants with a triage diagnosis of COPD and SAD status defined as R5–R20 > ULN will be invited for a cognitive interview regarding the new SADT-c questionnaire. Purposeful sampling will be used, to have a widespread of patient characteristics. If new items are added to the SADT-c questionnaire as a result of the cognitive interviews, 100 COPD patients that had previously completed the SADT-c questionnaire will be asked to complete the updated questionnaire.

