8.1 Primary study parameter(s)

The primary endpoint is the predictive value of SADT-c for SAD in COPD. The statistical hypothesis for the primary objective is that the predictive value of SADT-c is above the lower limit of the confidence interval of predictive value of SADT-a (AUC 0.74, LR+ 2.3 for the SADT-a bronze model). The hypothesis will be tested at a 2-sided significance level of 0.05.

For the analysis of this primary endpoint, the following population is defined:

- All participants that have a prior or novel COPD (triage) diagnosis, and
- Do not have an asthma, asthma-COPD overlap syndrome, missing or other diagnosis, and
- Have filled in the SADT-c questionnaire.

The presence of SAD will be based on oscillometry results. A resistance difference between 5 and 20 Hz (R5-R20) cutoff of 0.07 kPa x s x L⁻¹ will be used to define the presence of SAD¹⁵.

Analysis will be performed as done earlier for the development of SADT for asthma⁸. In short, to assess the predictive value of SADT-c we first will select the most important SADT items (secondary study parameter). Regression analysis will be used to select SADT items that show a relation with SAD in the expected direction based on the content validity of the items. In a next step the most important SADT items for SAD group will be selected by using logistic regression models. Prediction models using bootstrapping resampling will be used. In addition to the individual SADT items, also patient characteristics, such as age, sex, and height, BMI, will be considered as independent predictors in the model.

Selected key SADT items will be used together with available clinical information to build logistic regression models to predict the SAD group. Three levels of clinical information will be considered resulting in three regression models:

- Bronze: Basic patient characteristics (such as age, sex, age at diagnosis, BMI, or other)
- Silver: Spirometry test results (FEV₁ % predicted)
- Gold: Oscillometry test results (R5-R20 and reactance area (AX)).

For each model the area under the receiver operating characteristic curve (AUC), positive likelihood ratio (LR+) and sensitivity and specificity will be calculated, using a probability cut-off of 0.5 to indicate predicted SAD.

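### SADT-c is completed after oscillometry and forced spirometry, under conditions that differ by visit type and with no stated masking, so the primary predictor can be influenced by the testing

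*Protocol*

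**What the plan says.** Protocol section 6.2 fixes the order of the visit. For everyone: "After signing informed consent, the visit will include a (pre-)oscillometry measurement followed by a (pre-)spirometry measurement". Then: "In case of a diagnostic visit the participant will use Salbutamol followed by a post-oscillometry and post-spirometry measurement after a 15-minute wait time". The questionnaire is placed as follows: "During the wait time, or after the measurements in case of a control visit, the participant is asked to fill in the SADT-c questionnaire".

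The primary outcome comes from the same session. Section 8.1 states: "The presence of SAD will be based on oscillometry results". The measure is R5–R20, compared with the upper limit of normal in section 6.1.1 and with a fixed cutoff of 0.07 in section 8.1. Neither section says whether the value before or after salbutamol counts.

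Section 5.1 describes the SADT items as signs and symptoms, scored no, yes or unknown in the asthma version. The Figure 2 caption in section 5.2 mentions an example device report and a "Schematic overview of oscillometry process and decision support by the ALDS". No section says that participants or technicians are kept unaware of results until the form is complete, and none says that they are told.

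**The concern.** A symptom questionnaire that is meant to predict a test result is best answered before that test. Here it is always answered after some lung function testing, and two routes of influence are open.

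1. **Knowledge of a result.** A participant who learns that a measurement was abnormal may be readier to answer yes. This would create a link between items and SAD that would not exist when the tool is used without oscillometry.
2. **The testing itself.** Forced expirations, and salbutamol at diagnostic visits, may change how symptoms feel when the form is filled in. This route needs no disclosure.

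The stakes are the AUC, LR+, sensitivity and specificity of the primary endpoint, and also item selection, because section 8.1 picks items by their relation to SAD. About half of the planned 100 patients with COPD (the 50 newly diagnosed) would answer under diagnostic-visit conditions and the 50 with a known diagnosis under control-visit conditions. Section 3 describes one visit for all data collection, so answers given after testing cannot later be replaced by unaffected ones, and a statistical analysis plan cannot repair this.

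**Working it through.** **Order of events, from section 6.2**

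| | Diagnostic visit | Control visit |
|---|---|---|
| Before SADT-c | oscillometry, spirometry, salbutamol | oscillometry, spirometry |
| After SADT-c | second oscillometry, second spirometry | none stated |
| SADT-c after at least one oscillometry and one forced spirometry? | yes | yes |
| SADT-c after the oscillometry that defines SAD? | yes if the pre-salbutamol R5–R20 counts, no if the post-salbutamol value counts | yes |

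The third row holds for everyone. The fourth is settled only for control visits.

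**Comparison within the protocol.** Section 5 has the ACQ, CCQ and medical history questionnaire sent for completion before the visit. Section 6.3 separates the panel's two readings by at least four weeks and randomises their order, to prevent recall. SADT-c has no comparable protection.

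**Which way the AUC could move.** The protocol gives no figure for this, so there is nothing to reproduce. As an illustration, take one yes/no item with LR+ 2.3, the value reported for the SADT-a bronze model. Assumed, not in the document: sensitivity 0.46 and specificity 0.80.

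- Formulas: LR+ = sens / (1 − spec); single-item AUC = (sens + spec) / 2.
- Baseline: LR+ = 0.46 / 0.20 = 2.30; AUC = (0.46 + 0.80) / 2 = 0.630.
- Let a fraction d of no answers become yes. In patients with SAD, sens = 0.46 + 0.54d. If the same happens without SAD, spec = 0.80(1 − d).

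| d | SAD only: LR+, AUC | Both groups: LR+, AUC |
|---|---|---|
| 0.05 | 2.44, 0.644 | 2.03, 0.624 |
| 0.10 | 2.57, 0.657 | 1.84, 0.617 |
| 0.20 | 2.84, 0.684 | 1.58, 0.604 |

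Example for d = 0.10: sens = 0.46 + 0.054 = 0.514. With spec 0.80, AUC = 0.657. With spec 0.72, AUC = 0.617.

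**How much result-driven answering could add.** Take k independent items with no true link to SAD, a 50% yes rate without SAD and 50% + δ with SAD (assumed δ = 0.05 or 0.10). For the sum score, AUC = P(X₁ > X₀) + ½P(X₁ = X₀), with X₁ ~ Bin(k, 0.5 + δ) and X₀ ~ Bin(k, 0.5). For one item this is 0.5 + δ/2.

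The planned models also hold patient characteristics. So add the same items, by likelihood ratio, to an independent binormal score with AUC 0.74. Its separation is μ = √2·Φ⁻¹(0.74) = 0.91. With ℓ the log likelihood ratio of each item sum, AUC = ΣΣ P₁(i)P₀(j)·Φ[(μ² + ℓᵢ − ℓⱼ)/(√2·μ)].

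| k | Items alone, δ 0.05 / 0.10 | Added to a 0.74 score, δ 0.05 / 0.10 |
|---|---|---|
| 1 | 0.525 / 0.550 | 0.741 / 0.745 |
| 4 | 0.555 / 0.609 | 0.745 / 0.759 |

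So the same shift is worth 0.025 to 0.109 with nothing else in the model, and 0.001 to 0.019 on top of a score at 0.74.

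**The case against.** A reader might infer three stronger claims. The document supports none of them.

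- **Everyone answers after the measurement that defines SAD.** This is certain only at control visits. At diagnostic visits a second oscillometry follows the form, and sections 6.1.1 and 8.1 do not say which R5–R20 counts.
- **Participants know their result.** Disclosure would have to be inferred from silence and a figure caption. The caption names decision support and a report, but not when it appears, who sees it or whether it shows SAD.
- **The AUC is inflated.** That needs result-driven answering, which is possible but not shown. Symptoms provoked in both groups would lower the AUC. The protocol lists neither the SADT-c items nor their recall period, so susceptibility to recent exertion is unknown.

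It is also fair to say that the waiting time is a sensible slot for a form, that upward shifts shrink once other predictors are in the model, and that the gold model uses oscillometry anyway, so the argument about later use without a result concerns bronze and silver.

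These points limit what can be claimed about mechanism, direction and size. They leave the order of events, the lack of stated masking and the different answering conditions by visit type untouched. Convenience explains the slot only at diagnostic visits, since section 6.2 mentions no wait at control visits.

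**Conclusion.** The point holds as a low-cost improvement to conduct, not as a demonstrated bias. Section 6.2 places the self-reported primary predictor after at least one oscillometry and one forced spirometry in every participant, and after salbutamol at diagnostic visits only, with no stated masking. Influence on the answers is therefore possible.

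Its direction and size are unknown. The illustrations run from an AUC loss of 0.026 (0.630 to 0.604) to a gain of 0.054 (0.630 to 0.684) for a single item. For unrelated items added to a score already at 0.74, the gain is 0.001 to 0.019. All rest on assumed response shifts, and the single-item figures also on an assumed sensitivity and specificity. A biased item with a real link to SAD could behave differently.

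**What to change.** In section 6.2, have SADT-c completed directly after consent and before the first oscillometry, in both visit types. Add a sentence that lung function results are neither shown nor discussed with the participant until the form has been handed in.

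This covers both routes of influence. It also gives the two visit types the same answering conditions, and it makes the choice of R5–R20 value irrelevant to questionnaire timing. That choice still needs to be stated for its own sake.

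The cost is a few extra minutes at diagnostic visits, because the form no longer uses the 15-minute wait. The two rhinitis questions can stay where they are: they ask about diagnoses and feed the AC/DC tool, not the prediction of SAD.

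One limit remains. If an amended questionnaire is sent to the same 100 patients, those answers will come after testing whatever the visit order, and the report should say so.

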6.3 Determining the triage diagnosis using spirometry and oscillometry

To evaluate the spirometry and oscillometry results, a panel of ten experts on spirometry and oscillometry will review the pseudo-anonymized information from medical history, questionnaires and the respective lung function measurement. For each participant, three panel members (randomized) will initially review either the spirometry or the oscillometry reports, along with the medical history and questionnaires. After a minimum of four weeks, the same three panel members will review the remaining report (spirometry or oscillometry) for the same participant. The sequence of report delivery will be randomized to prevent panel members from recalling specific cases. This review flow is depicted in Figure 3.

Each of the 3 experts will individually determine a triage diagnosis for each patient. In addition, the expert will record the difficulty of diagnosis on a 6-point Likert scale from o to 5, in which o to 1 indicates easy to diagnose and 4 to 5 indicates hard to diagnose. In case only 2 out of 3 triage diagnoses are the same, the case will be reviewed by two additional experts. In case all triage diagnoses are different, the case will continue without additional review. In the statistical analysis those disagreements will be taken into account.

[figure not shown]

Figure 3. Flow of spirometry and oscillometry assessments by expert panel. * *The result can be either a spirometry or oscillometry measurement. The order will be randomly determined.*

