2. OBJECTIVES

Primary Objective:

1. To determine whether SADT-c can be used in patients with COPD to detect SAD.

Secondary Objectives:

- 2. To determine whether the bronze model SADT-a is predictive for SAD in COPD.
- 3. To develop SADT-c.
- 4. To evaluate how SADT-c compares to SADT-a.
- 5. To determine whether oscillometry and spirometry are equally effective for triage diagnosis in patients in primary care with respiratory symptoms.

Exploratory Objective:

Assess the diagnostic performance of the Asthma/COPD Differentiation Classification (AC/DC) Tool.

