3. STUDY DESIGN

The SCOOP-study will be executed in the Netherlands. The study consists of one visit during which all data will be collected. The aim is to include 200 participants in total. Of the 200 patients that will be seen for a visit, approximately 50 participants with previously diagnosed Chronic Obstructive Pulmonary Disease (COPD) and 150 participants without any diagnosis at the time of the visit will be invited. This should result in a total of 200 participants of which 100 are diagnosed with COPD: 50 with a pre-existing diagnosis and 50 newly diagnosed. An overview of the study flow is presented in figure 1.

Participants will visit the site for their usual care, which can be either a follow-up visit for those with an existing COPD diagnosis or a diagnostic visit. In addition to their usual care participants of the study will be asked to complete an oscillometry measurement and a Small Airway Dysfunction Tool for COPD (SADT-c) questionnaire. A panel of international experts will then review the oscillometry and spirometry reports of all 200 participants. Each report will be assessed by 3 to 5 independent pulmonologists in a randomized order. Finally, the triage diagnoses derived from oscillometry and spirometry assessments will be compared. The answers to the SADt-questionnaire items will be compared to the patients' respective SAD status to determine predictive value of SADT-c. Furthermore, ten to fifteen patients with COPD and SAD will be asked to participate in a cognitive interview to assess patient comprehension and necessity of additional questions. In case these are required, 100 COPD patients will be asked to complete the amended questionnaire.

[figure not shown]

Figure 1: Study flow for patients

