8.2 Secondary study parameter(s)

SADT-c

To determine whether bronze model SADT-a is predictive for SAD in COPD, the steps described in section 8.1 will be followed. The AUC, LR+ and sensitivity and specificity will be calculated and reported.

To assess the agreement between SADT-c and disease parameters, the steps described in section 8.1 will be reported. Logistic regression analysis results will be reported.

To assess the content validity and reliability of the SADT-c, 10-15 patients with COPD and SAD will be invited for a cognitive interview. Results will be presented in a descriptive way.

To evaluate how SADT-c and SADT-a compare in detecting SAD in COPD the predictive values of the various SADT-c and SADT-a models will be compared.

In case the SADT-c has a significantly reduced predictive value as compared to the SADT-a, new items derived from the cognitive interviews will be added, if any. The amended questionnaire will subsequently be reinvestigated using the same protocol, in the same population (ie. 100 patients with COPD participating in the SCOOP study).

Oscillometry vs spirometry

To assess the agreement between oscillometry and spirometry, triage diagnoses as determined by the expert panel will be compared. Cohen's kappa or comparable statistics will be used to compare the outcomes. Additional analysis will be done adjusted for difficulty of diagnosis and the agreement between panel members. In addition, subgroup analysis will be performed based on the level of agreement between panel members.

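### The oscillometry-spirometry comparison pools 50 known-COPD participants with the 150 undiagnosed patients the triage question concerns, and the panel rule leaves three-way splits without a panel diagnosis

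*Protocol*

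**What the plan says.** Objective 5 (Protocol Section 2) asks whether the two tests are "equally effective for triage diagnosis in patients in primary care with respiratory symptoms". Section 3 plans "approximately 50 participants with previously diagnosed Chronic Obstructive Pulmonary Disease (COPD) and 150 participants without any diagnosis at the time of the visit", expects 100 COPD cases in the end ("50 with a pre-existing diagnosis and 50 newly diagnosed"), and has the panel "review the oscillometry and spirometry reports of all 200 participants" before the resulting diagnoses are compared.

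Under Section 6.3, the same three experts read both reports of a participant at least four weeks apart. Each report comes with the history and questionnaire data, which according to Section 5 include medication. Section 6.2 schedules salbutamol and the repeat measurements for diagnostic visits only. Under Section 4.2, COPD is the only prior diagnosis that in itself qualifies a patient for entry.

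For disagreement among the three readers, Section 6.3 states: "In case only 2 out of 3 triage diagnoses are the same, the case will be reviewed by two additional experts". For a three-way split it states: "In case all triage diagnoses are different, the case will continue without additional review". It then says that the analysis will allow for such disagreements.

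Section 8.2 says that "triage diagnoses as determined by the expert panel will be compared", using Cohen's kappa or a similar statistic. It adds an analysis adjusted for difficulty and panel agreement, and subgroups by level of panel agreement. Section 8.3 uses the panel diagnosis again as the comparator for the AC/DC tool.

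**The concern.** There are two separate problems, both affecting the same comparison.

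**Case mix.** A quarter of the participants read by the panel already have a COPD diagnosis. A report without post-salbutamol data points to a control visit, and so to known COPD, whichever test is attached. The shared history and medication point the same way. Agreement on these participants may therefore reflect the common background information more than the interchangeability of the two tests. Section 9.3 hopes that equivalent effectiveness would reduce the burden of diagnostic testing. That inference needs agreement in patients who are still undiagnosed, and none of the analyses in Section 8.2 isolates them.

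**Adjudication.** Extra readers go to 2-1 cases, which already have a majority, and not to 1-1-1 cases, which have none. Section 8.2 compares panel diagnoses, but the visible text defines none for a 1-1-1 case, nor for a 2-2-1 result after five readers. The AC/DC comparison inherits the gap. If a split occurs in one modality only, that participant's two diagnoses rest on five readers and three.

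**Working it through.** **Composition (Section 3).** 50 + 150 = 200 participants and 50 + 50 = 100 COPD cases, as stated. Known COPD is 50/200 = 25% of the set. New COPD is 50/150 = one third of the undiagnosed.

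**Effect of the 50 on kappa.** The protocol gives no agreement rate, category frequencies or target kappa, so the inputs below are assumptions.

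kappa = (Po − Pe)/(1 − Pe), where Po is observed agreement and Pe is the sum of squared category shares (equal margins for both tests). Let c be the concordance in the 50, with discordant calls split evenly between the tests and the other categories.

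Three equally frequent categories, Po = 0.60 in the 150:

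- 150 alone: Pe = 3 × (1/3)² = 0.333; kappa = (0.60 − 0.333)/0.667 = 0.40.
- Add 50 with c = 1.00: Po = (90 + 50)/200 = 0.70; shares 0.50/0.25/0.25; Pe = 0.375; kappa = 0.325/0.625 = 0.52.
- c = 0.90: Po = 0.75 × 0.60 + 0.25 × 0.90 = 0.675; shares 0.4875/0.25625/0.25625; Pe = 0.369; kappa = 0.306/0.631 = 0.485.
- c = 0.60, the same as the 150: Po = 0.60; shares 0.45/0.275/0.275; Pe = 0.354; kappa = 0.246/0.646 = 0.38.

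The break-even is at c of about 65%. With c = 1.00, 50% agreement in the 150 moves kappa from 0.25 to 0.40, and 70% moves it from 0.55 to 0.64.

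Four categories are also plausible, since Section 8.1 mentions COPD, asthma, overlap and other. With shares 1/3, 1/3, 1/6, 1/6 and Po = 0.70 in the 150:

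| Set | kappa |
|---|---|
| 150 alone | 0.585 |
| all 200, c = 0.70 | 0.558 |
| all 200, c = 0.90 | 0.624 |
| all 200, c = 0.95 | 0.640 |
| all 200, c = 1.00 | 0.657 |

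**Effect of handling unresolved cases.** I simulated three readers, plus two more on a 2-1 split, with four categories. Unresolved means 1-1-1 or tied after five reads. Assumed reader accuracy was 0.85 on easy cases, 0.55 on hard cases (30% of the 150) and 0.95 on known COPD. Reads were independent given the true diagnosis, a simplification because the same experts read both reports.

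| Handling of unresolved cases | kappa, all 200 | kappa, 150 only |
|---|---|---|
| dropped | 0.95 | 0.94 |
| own category | 0.74 | 0.69 |
| counted as discordant | 0.70 | 0.64 |

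In this scenario about 14% of participants had a 1-1-1 result in at least one modality. The absolute values depend on the assumed accuracies. The gap between dropping and keeping was large in all eight accuracy settings tried: for all 200, kappa was 0.85 to 0.96 when dropped, 0.54 to 0.77 as a category and 0.46 to 0.72 as discordant.

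**The case against.** The strongest case on the other side is this.

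- The protocol never says that three-way splits are dropped. It says the analysis will allow for disagreement, plans analyses by panel agreement, and permits statistics other than kappa. The same experts read both reports, so a reader-level analysis could use every read. Coding of such cases can be left to the SAP, and the figure showing the review flow is not available here. This stands. A reader might infer that the panel rule inflates kappa, but inflation follows only if cases are dropped, which the text does not state.
- Higher agreement in known COPD is assumed. With equal agreement, pooling lowers kappa slightly (0.40 to 0.38, or 0.585 to 0.558). This stands too: upward bias is likely, not a fact.
- Prior diagnosis is not among the listed history items, and nothing says that readers are told it. The documents support known COPD being largely inferable, not that it is openly disclosed.
- Section 4.1 deliberately admits control visits, objective 5 says symptomatic rather than undiagnosed patients, and Section 8.2 names no analysis set. This has some weight. But Section 3 sends all 200 to the panel and compares the results, while triage diagnosis and diagnostic work-up concern patients not yet diagnosed.

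What the SAP may not be able to repair is the allocation of extra reads. That is an operational rule in Section 6.3, and a SAP finalised shortly before database lock could come too late to obtain reads that were never ordered.

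**Conclusion.** The point holds in a conditional form. The pooled comparison does not cleanly answer objective 5, because a quarter of the set has known COPD that readers can largely infer in both readings, and no planned analysis separates those participants. If agreement is higher in the 50, the pooled kappa overstates agreement in undiagnosed patients. Under the assumed inputs, the rise at 90-100% concordance is about 0.09 to 0.12 with three categories and 60% agreement in the 150, and about 0.04 to 0.07 with four categories and 70% agreement. If agreement is equal, kappa falls by 0.02 to 0.03.

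The adjudication rule is badly fixed as written: it spends extra reads where a majority exists and leaves 1-1-1 cases with no panel diagnosis for Sections 8.2 and 8.3. Its effect on kappa can be large but depends on handling that the protocol leaves open. It would be wrong to conclude that the protocol as written is certain to push agreement upward.

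**What to change.** **Section 8.2.** Make the 150 diagnostic-visit participants the primary set for objective 5. Report the known-COPD participants and the pooled 200 separately. For the 50, give raw agreement, since kappa is uninformative when nearly all fall in one category: at c = 0.90 in the three-category model, Pe = 0.95² + 2 × 0.025² = 0.904 and kappa = (0.90 − 0.904)/(1 − 0.904) = −0.04. Base the primary agreement on the same three reads per modality, and keep 1-1-1 as an undetermined category.

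**Section 6.3.** Send the two additional reads to cases without a majority. Use them only for the consensus panel diagnosis, which serves the AC/DC comparison and a sensitivity analysis of agreement. Keeping them out of the primary kappa avoids a conflict with the three-read rule. Code remaining ties as undetermined and state whether a 2-1-1-1 plurality counts as a diagnosis. Two extra reads give a 1-1-1 case a majority of five only if both match the same original reader, so some cases will stay undetermined.

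**Cost.** Wording and a wider confidence interval for kappa: roughly √(200/150) = 1.15 times as wide if the variance per participant is similar. No extra readers or participants are needed.
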